### 2.3.4 Medical and surgical history, prior and concomitant medication/procedures

All summaries will be done by treatment group based on the ITT population.

History of surgical events, medical conditions and any prior dermatological procedures or implants will be provided in a by-subject listing.

Prior (with stop dates prior to initial treatment) and concomitant medications (ongoing or with stop dates on or after initial treatment) for all randomized subjects will be provided in a by-subject listing. Prior and concomitant medications will be summarized using World Health Organization Drug Dictionary (WHO-DD) Anatomical-Therapeutic-Chemical (ATC) classification and preferred term (PT) for each treatment. The number and percent of subjects, and the number of drugs, will be summarized by ATC code. Concomitant medications that started due to an AE will be stated in indication.

## 2.4 Efficacy analysis

### 2.4.1 Datasets analyzed

The primary efficacy analysis of non-inferiority will be performed both on the ITT and the PP analysis set. Secondary efficacy will be performed based on the ITT population set.

### 2.4.2 Handling of missing data

Number of missing values will be summarized and reported as appropriate.

[REDACTED]

Impact of missing data on the primary analysis for Week 8 endpoint will be evaluated by performing sensitivity analysis based on the observed cases in the ITT population.

All other endpoints will be evaluated based on the observed cases in ITT, i.e. no imputations will be done.

### 2.4.3 Primary efficacy analysis

Non-inferiority will be established if the CI is entirely below 0.5 for both co-primary endpoints in both the ITT and PP populations. Superiority will be declared if the CI is entirely below 0 for both co-primary endpoints in both the ITT and PP populations. This decision criteria is consistent with a gate-keeping strategy (testing for superiority following the test for non-inferiority) to maintain the overall type I error rate at 5%.

#### 2.4.4 Secondary analysis

CIs for responders mentioned below will be calculated using normal approximation.

(i)

[REDACTED]

[REDACTED]

[REDACTED]

[REDACTED]

[REDACTED]

(iii)

[REDACTED]

[REDACTED]

[REDACTED]

[REDACTED]

(v) [REDACTED]

[REDACTED]

[REDACTED]

[REDACTED]

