4.1 General outline

This is a randomized, controlled, evaluator-blinded, multi-center study to evaluate the effectiveness and safety of *Restylane® Kysse* for lip augmentation and correction of perioral rhytids. Approximately 280 subjects will be randomized in a 2:1 ratio of treatment to control and treated. Approximately 187 subjects will be treated with *Restylane® Kysse* and 93 subjects will receive the control in the lips and perioral rhytids for 48-weeks. All randomized subjects' lips will have a MLFS score of 1 (Very Thin) or 2 (Thin). The upper lip and lower lip scores do not have to be equal as long as each score is 1 or 2.

At least 42 subjects enrolled and treated will be FST IV through VI. This includes up to 21 subjects with FST V to VI who do not have to meet the inclusion criteria for MLFS.

Investigator blinding will be accomplished by using a Treating Investigator to administer the treatments and a Blinded Evaluator, to whom randomization and treatment are concealed, to conduct the blinded assessments. Safety assessments will be performed by non-blinded personnel.

Eligible subjects randomized to receive treatment will be injected by the Treating Investigator at Day 1. The method of injection is at the discretion of the Treating Investigator and will be recorded. Sufficient amount of product should be injected to achieve optimal correction of the lips, in the opinion of the Treating Investigator and subject. Optimal appearance is defined as at least 1 MLFS step improvement from Baseline and best correction that can be achieved as agreed by the Treating Investigator and the subject. Touch-up treatment may be administered after 4 weeks if deemed necessary to obtain optimal aesthetic result; this decision should be agreed upon by the Treating Investigator and the subject. Touch-up treatment will not be performed if the subject has a disease or condition described in the exclusion criteria, or an ongoing treatment-related AE that in the opinion of the Treating Investigator would be worsened by a touch-up. It is recommended that the dose should not exceed 1.5 mL in each lip (including vermillion, vermillion border and cupid's bow) per treatment session. The study product may also be injected for optimal correction of the upper perioral rhytids, philtral columns, and/or oral commissures. The recommended maximum injected volume per subject and treatment is 6 mL (i.e. 3 mL for lips and 3 mL for perioral area).

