## 1 Study Information

### 1.1 Background

#### 1.1.1 Study design

This is a randomized, controlled, evaluator-blinded, multi-center study to evaluate the effectiveness and safety of *Restylane® Kysse* for lip augmentation and correction of perioral rhytids.

Approximately 280 subjects will be randomized in a 2:1 ratio of treatment to control and treated. Approximately 187 subjects will be treated with *Restylane® Kysse* and 93 subjects will receive the control in the lips and perioral rhytids and will be followed for 48-weeks.

[REDACTED]

Investigator blinding will be accomplished by using a Treating Investigator to administer the treatments and a Blinded Evaluator, to whom randomization and treatment are concealed, to conduct the blinded assessments.

Safety assessments will be performed by non-blinded personnel. Eligible subjects randomized to receive treatment will be injected by the Treating Investigator at Day 1.

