#### 1.1.2 Number of subjects and randomization

Approximately 280 subjects will be randomized to treatment or to control in a 2:1 ratio (treatment: control) stratified by FST (I-III, IV or V-VI) to achieve a total sample size of 234 evaluable subjects

[REDACTED]

Before starting the study, a randomization list will be prepared under the supervision of a designated statistician. Randomization will be performed using an Interactive Response System by assigning each subject to *Restylane® Kysse* or the control according to the randomization list.

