## 2 Statistical Methods

### 2.1 General methods

All statistical analyses, including summary tables and data listings, will be performed using the SAS® system (Version 9.3 or higher). Confidence intervals (CIs) will be two-tailed and constructed at a confidence level of 95%. P values will be two-sided and performed at a significance level of 5%.

All study data including observed and derived variables (e.g., change from baseline, response status) used in the summaries of analyses will be presented in by-subject listings. In general, efficacy, safety, demography, subject characteristics, and treatment related variables will be presented using descriptive statistics. For categorical parameters, the number and percentage of subjects in each category will be presented. The denominator for percentage will be based on the number of observations at that time point (i.e. observed cases). For continuous parameters, descriptive statistics will include number of observations, mean, standard deviation (SD), median, and range. Graphs will be used as appropriate.

Any change made to the finalized statistical analysis plan (SAP) after database lock will be documented in the Clinical Study Report (CSR).

For the primary analysis, non-inferiority will only be demonstrated if the CI is entirely below 0.5 for both co-primary endpoints in both the ITT and PP populations. Similarly, superiority will only be demonstrated if the lower confidence limit is entirely below 0 for both co-primary endpoints in both the ITT and PP populations. Therefore no multiplicity adjustment for Type I error is required.

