## 2.7 Determination of Sample Size

[REDACTED]. Accounting for approximately 15% drop-outs and non-evaluable subjects due to protocol deviations at week 8, a total of approximately 280 subjects will be randomized in the study. It is expected that the number of randomized subjects will be similar across the study sites.

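### Normal-approximation confidence intervals for response rates exceed 100% or collapse to zero width near the ceiling, and under-cover there; Wilson and Newcombe intervals would avoid this

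*SAP*

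**What the plan says.** SAP 2.4.4 opens with the only readable sentence on the method: "CIs for responders mentioned below will be calculated using normal approximation". SAP 2.1 sets the level: "Confidence intervals (CIs) will be two-tailed and constructed at a confidence level of 95"%. SAP 2.4.2 sets the data for everything except the primary endpoint: "All other endpoints will be evaluated based on the observed cases in ITT, i.e. no imputations will be done".

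The arm sizes are in SAP 1.1.1: about 187 subjects on Restylane Kysse, and "93 subjects will receive the control in the lips and perioral rhytids and will be followed for 48-weeks". SAP 1.1.2 gives the smaller evaluable total ("to achieve a total sample size of 234 evaluable subjects"), and SAP 2.7 explains the gap ("Accounting for approximately 15% drop-outs and non-evaluable subjects due to protocol deviations at week 8").

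The protocol synopsis defines response on the Medicis Lip Fullness Scale (MLFS) as a gain of one point or more from baseline, scored by the Blinded Evaluator. Protocol 4.1 describes the treatment target in nearly the same terms: "Optimal appearance is defined as at least 1 MLFS step improvement from Baseline", with an optional touch-up after 4 weeks. It also lets in some subjects outside the MLFS entry range: "This includes up to 21 subjects with FST V to VI who do not have to meet the inclusion criteria for MLFS".

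The remainder of SAP 2.4.4 is redacted. It cannot be seen whether the intervals are per arm, for the difference, or both, or whether there is a rule for rates near 100%.

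**The concern.** The usual normal-approximation interval for a proportion takes its width from the observed rate. As that rate approaches 1 the estimated standard error shrinks towards zero. The interval then runs past 100% or, when every subject responds, becomes a single point. In the same region the true coverage can fall well below the nominal 95%, and the smaller control arm suffers more.

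Early MLFS response is where this could happen. Subjects are treated until they have gained at least one step, and response is a gain of at least one point. No claim is made here for the wrinkle scale, the global aesthetic scale or late visits. What is at stake is how secondary results read in the study report, not the trial's success criteria.

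**Working it through.** **Arm sizes.** The plan's own figures fit together. 234/(1 − 0.15) = 275.3, against about 280 stated, and 280 × 2/3 = 186.7 and 280 × 1/3 = 93.3 give 187 and 93. Responder endpoints use observed ITT cases, so 187 and 93 are the natural early-visit sizes. The 234 evaluable also excludes protocol deviators. Split 2:1 (an assumption) it gives 156 and 78, used here only as a lower case.

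**Wald limits, no rate assumed.** The interval is p̂ ± 1.96 √[p̂(1 − p̂)/n]. For 91/93, p̂ = 0.9785, the half-width is 1.96 × √(0.9785 × 0.0215/93) = 0.0295, and the limits are 94.9 and 100.8%.

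| Non-responders | Upper limit, n = 93 | Upper limit, n = 187 |
|---|---|---|
| 0 | 100% (zero width) | 100% (zero width) |
| 1 | 101.0% | 100.5% |
| 2 | 100.8% | 100.4% |
| 3 | 100.4% | 100.2% |
| 4 | 99.8% | 99.9% |

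The pattern is the same at n = 78 and 156. Wilson intervals for comparison: 91/93 gives 92.5 to 99.4%; 184/187 gives 95.4 to 99.5% (Wald 96.6 to 100.2%); 93/93 gives 96.0 to 100%.

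**Rates assumed.** Two quantities follow from the binomial distribution. The first is P(0 to 3 non-responders), the chance of one of the outcomes above. The second is coverage, the sum of the binomial probabilities of every count whose interval contains the true rate.

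| Assumed true rate | P(0–3), n = 93 | P(0–3), n = 187 | Wald coverage, n = 93 | Wald coverage, n = 187 |
|---|---|---|---|---|
| 0.80 | ~0% | ~0% | 93.5% | 95.3% |
| 0.90 | 1.3% | ~0% | 90.3% | 92.9% |
| 0.95 | 31% | 1.5% | 94.3% | 90.3% |
| 0.97 | 70% | 19% | 93.9% | 91.7% |
| 0.98 | 88% | 48% | 84.5% | 88.5% |
| 0.99 | 99% | 88% | 60.7% | 84.4% |

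Coverage oscillates between tabulated rates, so averages over ranges are also useful:

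| Range of true rates | Wald, n = 93 | Wald, n = 187 | Wilson, n = 93 | Wilson, n = 187 |
|---|---|---|---|---|
| 0.80–0.97 | about 92.5% | 93.8% | 95.2% | 95.1% |
| 0.97–0.98 | 89.9% | 90.5% | 95.7% | 95.3% |
| 0.98–0.99 | 74.4% | 87.9% | 95.8% | 96.1% |

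In the first range Wald at n = 93 has an isolated low of about 79.5% near 0.968. In the last range Wilson's lowest value is 91.6% (n = 93). If the control arm fell to 78 and the rate were 0.99, Wald coverage would be 54.3%.

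**Between-arm difference.** By exact enumeration over both arms, Wald coverage with equal rates of 0.80 to 0.99 is 90.9 to 95.0% (187 vs 93) and 91.3 to 96.5% (156 vs 78). With unequal rates:

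| Kysse vs control | Wald, 187/93 | Wald, 156/78 |
|---|---|---|
| 0.99 vs 0.98 | 84.4% | 79.0% |
| 0.98 vs 0.99 | 95.1% | 95.4% |

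In the 0.99 vs 0.98 case, Newcombe gives 97.7% at both sizes, and Miettinen-Nurminen gives 94.0% and 94.8%.

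**Subjects exempt from the MLFS criterion.** They are at most 21/280 = 7.5%. If the other 259 respond at 0.99, the overall rate reaches 0.98 only if the 21 respond at (0.98 × 280 − 0.99 × 259)/21 = 0.857 or more. At 0.80 the overall rate is (259 × 0.99 + 21 × 0.80)/280 = 0.976.

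**The case against.** The strongest case against concerns weight, not arithmetic.

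- **Redaction.** Only one sentence of the method can be read. The hidden text may truncate limits or make an exception for sparse counts. This stands, so the finding can only be that no fallback is visible.
- **Reading of the term.** Plain Wald is the usual meaning, but no formula is given. A continuity correction would remove the exact zero width. At 187 and 93 and rates of 0.98 and 0.99, however, coverage would still be only 60.7 to 88.8%.
- **Assumed rates.** The documents give no expected response rate. Response is scored by a Blinded Evaluator who may not discuss treatment with the Treating Investigator or the subject, and the exempt skin-type V–VI subjects could pull the rate below 0.98. This stands for the coverage figures. It does not touch the limits that follow from counts alone.
- **Display against coverage.** Truncating at 100% would tidy the upper limit, and at a rate of 0.95 with n = 93 coverage is 94.3% even though 31% of trials would show one of the odd intervals. But truncation repairs neither the zero width nor the coverage nearer the ceiling.
- **Selectivity.** The 61% is a single cell (n = 93, rate 0.99); the other three cells at 0.98 and 0.99 are 84 to 89%. The large between-arm shortfall shown arises in one direction only, and other near-ceiling pairs at 187/93 do better (92.0% at 0.98 vs 0.97, 93.7% at 0.97 vs 0.98). Both points stand.
- **No decision depends on it.** Correct: the primary rules use change from baseline.

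**Conclusion.** The concern holds as a minor improvement to secondary reporting. Without any assumed rate, zero to three non-responders in an arm produce either a zero-width interval or an upper limit above 100%. The zero-width result depends on reading the SAP's term as Wald without continuity correction.

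At assumed true rates of 0.98 and 0.99, per-arm coverage is 61 to 89% at the planned sizes, and worst in the control arm. At ordinary rates the loss is modest. How much this matters in practice depends on whether early MLFS response is that high and on what the redacted text provides; neither can be settled from the documents.

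**What to change.** In SAP 2.4.4, replace the sentence on responder intervals with: *CIs for each arm's response rate will be Wilson score intervals; CIs for any between-arm difference in response rates will be Newcombe hybrid-score (or Miettinen-Nurminen) intervals.* One of the two difference methods should be chosen when the text is finalised. If the redacted text already covers rates near 100%, it should be aligned with this sentence.

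The cost is one sentence and a small programming change. Some intervals become slightly wider, and Wilson coverage can still dip to about 92% at single rates near 0.99. The design, sample size and primary analysis do not change.

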## 2.5 Safety Analysis

### 2.5.1 Extent of exposure

The number of subjects receiving initial treatment, touch-up treatment, and Week 48 retreatment respectively, will be presented by treatment group and treatment occasion (i.e. initial treatment or retreatment) as well as injection volume and other relevant injection characteristics, such as injection depth, injection method.

### 2.5.2 Adverse events

AE terms will be coded using MedDRA dictionary. A treatment-emergent AE (TEAE) is defined as an AE with a start date and time on or after the first study product injection. If relationship to treatment is missing, the event will be conservatively summarized as being related to study product. If intensity is missing, a separate category of missing intensity will be included in the summary table, and no imputation of intensity will be performed. Through the data cleaning process, all attempts will be made to avoid missing values for relationship and intensity.

All AEs will be presented in a by-treatment and by-subject listing, detailing the verbatim term given by the investigator, the preferred term (PT), system organ class (SOC), onset date, end date, intensity, outcome, relationship to study product, relationship to study product injection procedure, action taken with study drug, other action taken, affected treatment area, seriousness and criteria for seriousness. Serious AEs will be presented in a separate listing.

Time to onset of an AE will be derived as the start date minus date of most recent treatment. If the start date is missing, it will be assumed that the AE started on the day of most recent treatment.

Duration of an AE will be derived as the stop date minus the start date + 1. If the start date is missing, it will be assumed that the AE started on the day of most recent treatment. Missing stop date will not be imputed and therefore no duration will be calculated in these cases. Instead, the number of AEs that were ongoing at the end of the study will be given.

An overall summary of AEs will be presented by treatment. The summary will include the total number of events, frequency counts and percentages of subjects with:

- Any TEAE

- Any AE related to product and/or injection procedure
- Unrelated TEAEs
- No TEAEs reported

Summaries of related AEs (including the total number of events, frequency counts and percentages of subjects) will be displayed by treatment and treatment occasion according to the following:

- All AEs by SOC and PT in descending order of frequency (the combined frequency of both treatments)
- All AEs by SOC, PT, and maximum intensity (mild, moderate, or severe)
- All AEs by SOC, PT, and action taken (none, medical treatment, non-pharmacological treatment, subject withdrawn)

For related AEs, the number of days to onset and duration of event will be summarized by SOC and PT, using mean, SD, minimum, maximum, and median statistics.

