Subjects will have in-clinic follow up visits at 2, 4, 8, 16, 24, 32, 40, and 48 weeks after the last injection. If a touch-up is performed, a second 2-week and 4-week follow-up visits should be scheduled. At the 48-week visit after all study procedures for the visit are completed, subjects can receive an optional additional treatment if optimal aesthetic improvement is not maintained with *Restylane® Kysse*. If re-treatment is performed, a second 2-week and 4-week follow-up visits should be scheduled. In addition to the clinic visits, phone visits will also occur as specified in the study flow chart below.

A Study Flow Chart is provided on the next page.

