8.7.4 Reporting of adverse events

Adverse event reporting on each subject shall start at screening visit after the signature of the ICF. The reporting shall continue during each follow-up visit (including telephone contacts and extra visits between planned visits) until the last scheduled visit in the study.

All AEs, non-serious as well as serious, are to be reported as an AE in the eCRF.

Follow-up information and data missing in the initial SAE reporting shall be gathered as soon as possible and reported immediately but not later than 24 hours of awareness of the new data. Complete and adequate information on each SAE is required. All attempts to obtain this information, including dates for follow-up activities, must be documented by the Investigator or designated study staff.

Supporting documentation to be provided with the SAE report:

- Concomitant medication form
- Concomitant procedure/treatment form
- AE form
- Medical history form
- Any other relevant supporting documentation (e.g. hospital notes, death certificate, autopsy reports etc.)

The SAE form must be signed and dated by the Investigator. If the initial 24-hour SAE report does not contain full information or if it is made without using the SAE form the fully completed and signed SAE form shall be e-mailed to the Sponsor. A copy of the fully completed SAE form shall be kept at the site.

In addition, the Investigator shall report SAEs to the responsible IRB without undue delay, if applicable according to national regulations. The Investigator is responsible for checking what reporting procedures are applicable for his/her IRB regarding SAEs and final report of the outcome of the study and to comply with such reporting procedures during the study period. For non-urgent complementary information not possible to send by e-mail or fax, please use surface mail.

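### The overall adverse event summary is not split by treatment occasion, so events after the optional Week 48 retreatment are mixed into its all-cause comparison of the arms

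*SAP*

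**What the plan says.** For the overview, SAP 2.5.2 states: "An overall summary of AEs will be presented by treatment". It gives numbers of events and of subjects in four rows: any treatment-emergent event, any related event, unrelated treatment-emergent events, and none reported.

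The window is set in the same section: "A treatment-emergent AE (TEAE) is defined as an AE with a start date and time on or after the first study product injection". No closing date is given, and nothing cuts the window at Week 48 or at retreatment.

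The paragraph after the overview treats related events differently. Their summaries "will be displayed by treatment and treatment occasion according to the following". SAP 2.5.1 shows what an occasion is: exposure "will be presented by treatment group and treatment occasion (i.e. initial treatment or retreatment".

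Protocol 4.1 provides that, once the Week 48 procedures are complete, "subjects can receive an optional additional treatment if optimal aesthetic improvement is not maintained". It adds: "If re-treatment is performed, a second 2-week and 4-week follow-up visits should be scheduled". Under Protocol 8.7.4, adverse event reporting runs "until the last scheduled visit in the study".

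**The concern.** Up to Week 48 the overview compares randomised arms. After Week 48 it also includes a period that only some subjects enter. Entry depends on the subject's choice and on whether the effect has lasted, and both arise after randomisation. Retreated subjects have another injection and additional follow-up in which events can be recorded. If uptake differs between arms, the all-cause percentages can differ even when the two products are equally safe. The event totals are affected too, because a later event adds to the count even in a subject who already had one.

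The SAP already separates the two periods for related events, so the overview is out of step with its own section.

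A second ambiguity bears on the control column. Protocol 4.1 names the investigational product at the end of its retreatment sentence. That can be read as the product given at retreatment, or as the product whose effect was not maintained. On the first reading, a subject randomised to control could contribute events after the other product. The as-treated rule in SAP 2.2 does not say how to classify such a subject. The passages need to be reconciled. The main point stands under either reading.

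**Working it through.** **Do events after retreatment enter the overview?** They start after the first injection, so they meet the definition in SAP 2.5.2. They fall within the reporting period of Protocol 8.7.4, because retreatment brings its own 2-week and 4-week visits. No visible text removes them or tabulates all-cause events by occasion. They are therefore included.

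**Which rows are affected?** All four pool the periods. The related row can be recovered from the by-occasion tables. The any, unrelated and none rows cannot be recovered from any visible summary; the row for none mirrors the any row.

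**How large could the effect be?** The plan states no figure to reproduce. All rates and uptakes below are assumptions. Let *b* be the risk of an event before retreatment (the same in both arms), *f* the share retreated, and *s* the risk of an event after retreatment among subjects who had none before. Then

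- pooled risk = b + (1 − b) × f × s
- false difference between arms = (1 − b) × (f₂ − f₁) × s

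With equal uptake, f₂ − f₁ = 0 and the false difference is 0. The rest takes f₁ = 50% and f₂ = 70%.

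*Follow-up after retreatment.* The minimum is 4 weeks (Protocol 4.1). An upper value takes the 15.0 months of Protocol 4.3 as fully used: 65.2 weeks − 4.3 (30-day screening) − 4 (touch-up) − 48 = 8.9, or about 9 weeks.

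*Unrelated row.* Assume a constant rate, so s = 1 − (1 − b)^(w/48) for w weeks of follow-up. For b = 30%:

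- 4 weeks: s = 1 − 0.7^(4/48) = 2.9%; false difference 0.7 × 0.2 × 2.9% = 0.41 points
- 9 weeks: s = 1 − 0.7^(9/48) = 6.5%; false difference 0.7 × 0.2 × 6.5% = 0.91 points

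| Assumed risk by Week 48 | 4 weeks | 9 weeks |
|---|---|---|
| 20% | 0.29 | 0.66 |
| 30% | 0.41 | 0.91 |
| 40% | 0.50 | 1.10 |
| 50% | 0.56 | 1.22 |

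(False difference in percentage points.)

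*Any-event row.* Assume b = 40% and s = 20% to 40%, since an injection brings related events:

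- s = 20%: 0.6 × 0.2 × 0.20 = 2.4 points (46.0% against 48.4%)
- s = 40%: 0.6 × 0.2 × 0.40 = 4.8 points (52.0% against 56.8%)

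*Scale.* With 187 and 93 subjects (SAP 1.1.1), the standard error of a difference near 30% is √[0.21 × (1/187 + 1/93)] = 5.8 points. Near 50% it is √[0.25 × (1/187 + 1/93)] = 6.3 points.

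**The case against.** The table is descriptive, and no test of adverse events appears in the visible text. A count over all exposure in the study is a legitimate safety quantity. Related events are already split by occasion, every event is listed by subject with its onset date, and the number retreated is reported by arm, so a reader can see the factor that would distort the overview. The part that no summary recovers is mainly the unrelated row, where a split by occasion tells least. On the assumptions above, the false difference there is at most about a fifth of a standard error, and in the any-event row it is below one standard error. The 9-week follow-up is inferred, not stated. Parts of Protocol 10.5 and SAP 2.5.5 are blacked out and the list in SAP 1.6 is not visible, so a split could be specified there.

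Most of this stands, and it is why the point is minor. It does not remove the point. A small artefact relative to sampling error is still an artefact. A listing permits a split but does not plan one, so the split would be chosen after the data are seen. The wording in SAP 2.5.2 that sets up this table is complete and does not include occasion.

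**Conclusion.** The concern holds as a low-severity matter of presentation. Followed as written, SAP 2.5.2 mixes a randomised period with a self-selected one in the all-cause rows of the overview. No effectiveness conclusion or visible safety test is affected.

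The size cannot be derived from the documents. For assumed uptake of 50% against 70%, the unrelated row would shift by about 0.3 to 1.2 points. The any-event row would shift by 2.4 to 4.8 points, mostly through related events that the related-event tables already show by occasion. A false difference arises only if uptake, or risk after retreatment, differs between arms. Because uptake depends on how well the effect is maintained, a difference is plausible, but the documents do not establish one. The reading that no split exists is limited to the visible text.

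**What to change.** In SAP 2.5.2:

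- Present the overall summary by treatment and treatment occasion, as the related-event tables already are.
- Limit the between-arm version to events starting before the Week 48 retreatment, that is, the initial and touch-up period.
- Tabulate events starting on or after retreatment separately, by product actually injected.
- Keep the whole-study total alongside.

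The retreatment sentence in Protocol 4.1 and the as-treated rule in SAP 2.2 should also be reconciled, so that it is clear how a retreated subject is classified.

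The cost is a few words and one extra table. No new data are needed: onset dates are already listed, and the SAP already links events to the latest injection ("Time to onset of an AE will be derived as the start date minus date of most recent treatment").
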